Lab Sessions 2-5 will each include a preference task in which two products are available. In the sampling phase, participants will sample and then rate the same combusted cigarette type from Lab Session 1 and will also sample and rate an e-cig with the assigned combination of characteristics for that session (i.e., 3 mg/mL nicotine + cigarette flavor; 3 mg/mL nicotine + non-cigarette flavor; 18 mg/mL nicotine + cigarette flavor; or 18 mg/mL nicotine + non-cigarette flavor). E-liquid nicotine concentration will be administered under double-blind conditions; flavors, by necessity, will not be blinded. In the preference phase, participants will be prompted via computerized instructions to make a series of 10 choices. Each choice will be to either take 2 cigarette puffs, 2 e-cig puffs, or to abstain from puffing; again, a total of 20 puffs (from either or both products) is available (tasks are described in greater detail below). Between lab sessions, participants will be instructed to return to their usual tobacco use patterns.

Design Schematic					
NNC cigarettes (n=60): 5 sessions			VLNC cigarettes (n=60): 5 sessions		
e-liquid nic concentration	e-liquid flavors	e-liquid flavors	e-liquid nic concentration	e-liquid flavors	e-liquid flavors
3 mg/ml	x	x	3 mg/ml	x	x
18 mg/ml	x	x	18 mg/ml	x	x
No e-cig	x		No e-cig	x	

Summary of Measures

MEASURES	SCREEN/ BL	LAB SESSIONS				
		1	2	3	4	5
QUESTIONNAIRES AND MONITORING						
Demographics Questionnaire	X					
Medical History Questionnaire & Follow-Up Questionnaire	X					
MINI Suicide Subscale	X					
Tobacco Use History Questionnaire	X					
Vaping History Questionnaire	X					
Timeline Follow Back (TLFB): Baseline and Lab Session Versions	X	X	X	X	X	X
Contemplation Ladder	X					
Drug Use History Questionnaire	X					
Depressive Symptoms (CES-D)	X					
Fagerstrom Test for Nicotine Dependence (FTND)	X					
Cigarette Dependence Questionnaire	X					
Environmental Tobacco Smoke (ETS) Questionnaire	X					
Smoking/Vaping Identity	X					
Smoking Expectancies Questionnaire	X					
Respiratory Health (ATSQ)	X					
Predicted Behavior Interview						X
Adverse Events		X	X	X	X	X
End of Study Questionnaire						X
LABORATORY PREFERENCE TASK						
Questionnaire on Smoking Urges (QSU)- Brief	X	X	X	X	X	X
Minnesota Nicotine Withdrawal Scale (MNWS)	X	X	X	X	X	X
Positive and Negative Affect Scale (PANAS)	X	X	X	X	X	X
Cigarette Evaluation Scale (CES)	X	X	X	X	X	X
Vaping Expectancies Questionnaire (VEQ)	X					

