The following screening assessments will be administered via Qualtrics or REDCap, web-based data collection platforms hosted by the University of Minnesota's CTSI:

- 1) Demographic History Questionnaire, which will assess age, gender, ethnicity, race, education, income, marital status, living situation, and employment history.
- 2) Center for Epidemiological Studies-Depression Scale (CES-D; Radloff, 1977), which measures symptoms of depression
- 3) Contemplation Ladder (Abrams, et al., 2003) to assess intention to quit smoking.

In the event that the Qualtrics/REDCap websites are not functioning, the assessments will be printed out and administered on paper. The source documents will be kept in the participant's binder. The interviewer will enter the data into Qualtrics/REDCap when it resumes functioning properly. This information should be recorded in the 'End of Visit Evaluation Form' and entered in to REDCap.

Eligibility Determination

Research staff will determine initial eligibility after reviewing all eligibility criteria except for the medical/psychiatric history. Researchers will pay ineligible participants \$35 for their time spent completing the screening assessments. The LMP will not review the medical history forms of participants who are not eligible for other, non-medical reasons.

If the participant is deemed eligible, then she/he will provide saliva and urine samples, complete the Baseline assessments, and be scheduled for Lab Session 1. They will receive \$70 for completing both the Screening and Baseline procedures. Participants will be instructed to use tobacco products as they normally would between the Screening/Baseline visit and the night before Lab Session 1; participants should not use any tobacco products on the day of Lab Session 1.

Final eligibility of the participant will be determined by a licensed medical professional (LMP) after reviewing the Brief Medical History Questionnaire, Medical History Follow-Up Questionnaire and the MINI suicide subscale. If the participant's score on the CESD indicates elevated symptoms of depression, then the CESD will be submitted to the LMP for review as well. The LMP will sign off prior to Lab Session 1 that the participant is medically stable to use the study product(s). If the LMP determines a participant is not medically stable enough to continue in the study, then the researcher will contact the participant prior to Lab Session 1 to cancel the lab visit.

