At the end of the Screening/Baseline Visit, the researcher will complete the End of Visit Evaluation Form, which will be entered into REDCap. This will allow the researcher to make note of any problems encountered during the visit, to track which computers were used for which tasks, and to note any concerns about the validity of the participant's self-report of tobacco use.

Suicidality/Mental Health Monitoring

Participants who indicate a suicide attempt in the past 2 years on the MINI Suicide Subscale will not be eligible to participate in the study. The participant will be paid \$35 and provided with local mental health resources. The LMP/on-site clinician will be available by phone for consultation within 24-hours. If the participant has attempted suicide between 2-10 years ago, then the LMP will have to approve eligibility.

The following suicidality/mental health monitoring protocol is being used by CAAS researcher [name] who is also conducting an adolescent smoking study:

If the participant has stated that they are currently feeling suicidal or have thoughts of hurting themselves, the RA should call the study LMP/clinician ([name], or another CAAS clinician if [name] is not available). Specifically, this safety plan will be triggered by a positive response to any item on the MINI Suicide Subscale.

[name] will ask the following questions and document the participant's responses. Assess the situation in a calm, matter-of-fact tone. Gather and document as much information as possible. [name] will ask the following questions:

- *You mentioned that you have been thinking about death and/or committing suicide. Could you tell me a little more about these thoughts?*
- *Have you ever made any suicide attempts before?* Try to get information on how many times, how long ago, what he/she did, and what happened.
- *Do you have a plan now?* Assess if the subject has a plan, a way to carry out the plan, and an intention to carry out the plan. Try to determine relevant details, such as: Does the subject live alone? Will they have the opportunity to carry out the plan?
- *Do you have a therapist, counselor, or doctor that you talk to on a regular basis?*
IF YES: *What is that person's name?*

IF NO: *Have you discussed this with a friend or family member?*
IF YES: *What is his/her name*
- See if the subject will contract to not hurt themselves.

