If the participant has indicated a current plan to commit suicide, but the LMP/study clinician has determined that immediate action is not required (no means or intent to carry out the plan) the LMP/study clinician will call them the next day to check on how they are feeling and provide them with the contact number for the Samaritans.

If the LMP/study clinician indicates that immediate action is required, let them know that the LM/clinician has their very best interest in mind and that also this situation requires that we contact the appropriate personnel in order to help protect their well-being. **Call 911** to inform emergency personnel of the situation at the most appropriate time, either while still in the presence of the participant or immediately after you leave them.

- If the participant reports current intent to commit suicide, contact the participants' parent or guardian on file (if a minor) AFTER calling 911.

Inclusion Criteria:

- 1) Ages 15-20
- 2) Daily or near daily smokers for 3 months or more
- 3) Must have used an electronic nicotine device on a minimum of two lifetime occasions.
- 4) Breath CO levels > 5 ppm (if ≤ 5 ppm, then NicAlert Strip = ≥ 3) or positive result on a comparable cotinine test (NicConfirm or IDTC Rapid Nicotine)
- 5) Speak, comprehend, and read English well enough to complete study procedures

Exclusion Criteria:

- 1) Unwilling to use research cigarettes or vaping device as part of the study
- 2) Intention to quit smoking in the next 30 days

- 3) Using tobacco products (other than cigarettes, vaping devices, or roll-your-own tobacco) ≥ 15 days in the past 30 days.
- 4) Any medical or psychiatric condition in which participation is likely to pose a significant threat to health or for which the condition could interfere with the ability of the participant to fully participate (as determined by the LMP)
- 5) Self-reported illicit use of any drug except marijuana ≥ 10 days in the past 30 days
- 6) Binge drinking alcohol (≥ 10 days in the past 30 days, $\geq 4/5$ drinks in a 2-hour period (female/male))
- 7) Pregnant or breastfeeding
- 8) CO reading > 80 ppm
- 9) Systolic BP outside the range of 90-159, diastolic BP outside the range of 50-99, or heart rate outside the range of 45-104. Participants failing for any of these criteria will be allowed to re-screen once per criterion.

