- 10) Indicating Yes on Questions 4-6 on the MINI or with a suicide attempt in the past 2 years (if within the past 2-10 years, LMP approval required).
- 11) Having participated in another research study during the past year in which they were switched to research cigarettes for longer than one week.
- 12) Self-reported allergies to propylene glycol, vegetable glycerin, nuts, or chemicals used to flavor food products.
- 13) Adverse reactions when previously using vaping devices.

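### The safety plan allows the 911 call to be made just after staff leave a participant who needs immediate action, and no suicidality-specific question is described after Screening/Baseline

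*Combined protocol and SAP*

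**What the plan says.** **When immediate action is needed.** Under Suicidality/Mental Health Monitoring, the LMP or study clinician decides whether immediate action is required. If it is, staff tell the participant and call 911 at whatever time is most appropriate, "either while still in the presence of the participant or immediately after you leave them". Where a minor reports current intent, the parent or guardian is contacted only after 911.

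**What starts the plan.** A participant who states current suicidal feelings or thoughts of self-harm prompts a call to the clinician. The next sentence narrows this: "Specifically, this safety plan will be triggered by a positive response to any item on the MINI Suicide Subscale". The clinician's questions include "Do you have a plan now". If there is a plan but no means or intent, "the LMP/study clinician will call them the next day to check on how they are feeling".

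**Who may enrol.** Exclusion criterion 10 removes those "Indicating Yes on Questions 4-6 on the MINI or with a suicide attempt in the past 2 years". For older attempts: "If the participant has attempted suicide between 2-10 years ago, then the LMP will have to approve eligibility". Under Eligibility Determination, the LMP reviews the MINI before Lab Session 1, and the CES-D as well if it is elevated.

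**What is asked later.** In the Summary of Measures, the row "MINI Suicide Subscale" is marked at Screening/Baseline only. The interview lists for Lab Sessions 1-5 hold concomitant medications, the Health Changes Questionnaire, the adverse event form and the TLFB. Health Changes asks about negative change in physical or mental health and about any medical care received (Identifying Adverse Events). The 30-day call is described as covering smoking, tobacco use and open adverse events.

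**The concern.** The 911 rule applies only after a clinician has judged that waiting is unsafe. At that moment leaving first is an expressly permitted option, and no instruction says to stay. Because the parent of a minor with current intent is called after 911, a 15- to 17-year-old could be alone before either call is made.

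The second matter is a mismatch between detection and follow-up. The protocol treats any positive MINI item as serious enough for a clinician call, yet excludes on a narrower set of answers. It can therefore identify an adolescent as needing assessment, enrol that person, and describe no direct question afterwards. The only later contact that the safety plan itself names is the single next-day call, limited to people with a current plan.

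What is at stake is participant safety in a study of 15- to 20-year-olds, not the validity of its results.

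**Working it through.** The plan gives no figure to reproduce. The check compares sections, followed by simple counts.

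**1. The 911 rule.** Sequence in the text: clinician directs immediate action; participant is told; 911 is called in the participant's presence or immediately after staff leave; parent is contacted after 911 if a minor has current intent. Nothing elsewhere in the documents removes the second option or requires continued observation.

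**2. Who can be flagged and enrolled.**

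| Screening finding | Safety plan starts? | Excluded by criterion 10? |
|---|---|---|
| Yes on MINI Questions 4-6 | Yes | Yes |
| Yes on another MINI item only | Yes | No |
| Attempt within 2 years | Yes, if a MINI item records it | Yes |
| Attempt 2-10 years ago | Yes, if a MINI item records it | No, if the LMP approves |

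The second and fourth rows are the flagged group.

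**3. What reaches them later.**

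- New or worsening symptoms: Health Changes, at 5 of 5 lab sessions.
- A treated attempt or a psychiatric admission: the medical-care question, at the same sessions.
- Ideation that is volunteered: the first trigger sentence, which is not tied to a visit.
- Ideation that is unchanged: a truthful answer about negative change can be no. The adverse event rules also need no new form for a pre-existing condition that has not increased in severity or frequency, unless it otherwise meets the definition.
- An attempt neither treated nor volunteered: no described question names it, although Withdrawal or Monitoring of Participants requires immediate withdrawal. Pregnancy is on the same withdrawal list and is tested at every visit.
- PANAS and MNWS are repeated, but nothing links them to the safety plan.

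**4. Time since the only MINI.** Inputs: Lab Session 1 falls 3 to 21 days after screening. Later sessions are at least 48 hours apart, ideally within one week for Sessions 2-4. The call comes 25 to 35 days after Session 5.

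- Shortest, to Lab Session 5: 3 + 4 × 2 = 11 days.
- Shortest, to the call: 11 + 25 = 36 days.
- Upper ends of the stated windows, to Lab Session 4: 21 + 3 × 7 = 42 days.
- Lab Session 5 has no stated upper limit. If the one-week ideal is carried over (assumption): 21 + 4 × 7 = 49 days, and 49 + 35 = 84 days to the call.

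**5. Workload of a targeted question.** The size of the flagged group is not given. Assume 5% to 20% of 120 completers, six contacts each (five sessions and the call), and 2 to 5 minutes per contact.

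| Flagged share | People | Questions | Staff hours |
|---|---|---|---|
| 5% | 120 × 0.05 = 6 | 6 × 6 = 36 | 36 × 2/60 = 1.2 to 36 × 5/60 = 3 |
| 20% | 120 × 0.20 = 24 | 24 × 6 = 144 | 144 × 2/60 = 4.8 to 144 × 5/60 = 12 |

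Drop-outs would add to this, since enrolment continues until 60 per group complete.

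**The case against.** Much is already in place: the MINI, LMP review and sign-off, clinician questioning on any positive item, exclusion for unstable psychiatric conditions, a mental-health question at every lab session, medical review of adverse events, and mandatory withdrawal for an attempt or psychiatric hospitalization. An attempt years ago is history, not current ideation. The wording of MINI Questions 4-6 is not given, so the flagged group might contain nobody with current ideation. All of this stands, and it is why the second point is modest.

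The 911 text also deserves a fair reading. It says immediately, it asks for the most appropriate time, and it already allows the call in the participant's presence. Any delay should be short. But the option to leave first remains, and the benefit of keeping it is not explained.

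A reader might infer that suicidality goes unmonitored after screening. The documents do not support that: Health Changes and volunteered statements operate throughout, and the End of Study Questionnaire, the 30-day call script and the Adverse Event SOP are not reproduced. The supportable statement is that no suicidality-specific question is described. A reader might also infer that overnight abstinence raises suicide risk. The protocol lists depressed mood among withdrawal symptoms but calls them temporary and usually mild, and nothing shows a raised risk.

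Two practical objections shape the remedy. During COVID-19 the research assistant works from a separate room by Zoom, so an instruction to remain in the room would conflict with that set-up. And a question placed before the pre-task MNWS, QSU and PANAS could affect secondary-aim measures or delay the choice task.

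**Conclusion.** The 911 point holds on the text alone and needs no assumption: as written, the rule permits a participant judged to need immediate action to be left before help is called.

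The follow-up point holds in limited form. The MINI is scheduled at 1 of 6 in-person visits, and no later suicidality-specific question is described, while some MINI-positive adolescents and some with older attempts may enrol. The residual gap is unchanged or unvolunteered ideation, or an untreated and unvolunteered attempt, in that subgroup over at least 11 days to Lab Session 5 and 36 to the call. The subgroup's size is unknown; 6 to 24 people is an assumption used only to cost the remedy. The conclusion also depends on the unseen instruments and the SOP containing no such question.

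This is a participant-safety improvement and does not bear on the primary endpoint, power or analysis.

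**What to change.** 1. **911 call.** In Suicidality/Mental Health Monitoring, delete the option to call after leaving. State that staff keep the participant under continuous observation, in person, through the one-way mirror or by Zoom (or stay on the line if by phone), while 911 is called and until help arrives.

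2. **Trigger.** Replace the narrowing sentence with: *This safety plan applies at any study contact when current suicidal feelings or thoughts of self-harm are reported, including in a Health Changes answer, and at Screening/Baseline on a positive response to any MINI item.*

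3. **Targeted question.** Have the LMP sign-off record who is flagged. At each lab session, after the post-task CO and before the participant leaves, and again at the 30-day call, ask flagged participants and anyone reporting a negative mental-health change: *Since our last contact, have you had thoughts of suicide or of hurting yourself, made a plan, or made an attempt? Do you have such thoughts or a plan now?* A new or current positive answer goes to the clinician under the safety plan. The full MINI need not be repeated.

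Asking at the end of the session leaves that session's choice task, MNWS, QSU and PANAS untouched. Its drawback is that ideation not mentioned earlier surfaces only after the task; item 2 ensures that anything disclosed at the start is acted on at once.

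**Cost.** A protocol amendment, brief staff training and, on the assumptions above, about 1.2 to 12 staff hours over the study, plus questions prompted by a reported mental-health change. A clinician must be reachable by phone during session and call hours; the availability within 24 hours stated for participants excluded after a recent attempt would be too slow. Item 1 needs only a wording change and can be adopted by itself.

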- 6) Perceived Health Risks Scale (PHRS; Hatsukami et al., 2015), a measure of the perceived addictive potential and other health risks associated with cigarettes
- 7) Positive and Negative Affect Schedule (PANAS; Watson, Clark, & Tellegan, 1988), which measures symptoms of positive and negative affect
- 8) Minnesota Nicotine Withdrawal Scale (MNWS; Hughes & Hatsukami, 1986), a measure of nicotine withdrawal
- 9) Questionnaire of Smoking Urges-Brief – Usual Brand Cigarette (QSU; Cox, Tiffany, & Christen, 2001; Tiffany & Drobes, 1991), which measures the urge to smoke
- 10) Cigarette Evaluation Scale (CES; Westman, Levin, & Rose, 1992; Cappelleri, et al., 2007), which measures responses to cigarettes (e.g., reward, satisfaction)
- 11) Smoking Expectancies Questionnaire, which will be used to understand factors that motivate adolescents to smoke cigarettes.
- 12) Vaping Expectancies Questionnaire (VEQ), which assesses participant's expectancies regarding the use of vaping devices
- 13) Vaping Device Utility Questionnaire, an assessment of the reasons for using vaping devices
- 14) Cigarette Purchase Task – Usual Brand Version (Jacobs & Bickel, 1999; MacKillop et al., 2008) which will be used to generate cigarette demand curves. Participants will be asked to report the number of cigarettes that they would consume in a day at various costs. Several indices of demand are generated from the raw values, including demand intensity (consumption at zero price), Omax (maximum amount of money allocated to cigarettes), breakpoint (the first price at which a subject reports zero consumption) and Pmax (the price at which Omax occurs). This task will indicate whether prolonged VLNC cigarette use reduces cigarette demand and increases sensitivity to increases in cigarette costs.

Biological specimens collected, stored, and entered into CENIC Biosample Collection Platform:

- 1) **Saliva sample for NMR assessment:** Participants will be asked to provide two saliva samples during Baseline for assessment of nicotine metabolite ratio (NMR), an indicator of CYP2A6 enzyme activity (Benowitz, et al., 2003). Participants must wait 30 minutes after arrival to the lab before collecting the two saliva samples. During this time, participants cannot eat, drink, chew gum or smoke cigarettes. Samples will be stored at temperatures no more than -20°C. Saliva samples will be sent regularly to be analyzed and stored at the University of Minnesota.

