In the *Sampling Phase* (~20 min), participants will be oriented to task procedures and shown the products available for that session. In Lab Session 1, only one product - NNC or VLNC cigarettes - will be available. Once the task begins, all instructions will be delivered via computer; sessions will be continuously observed by a research assistant through a one-way mirror. Participants will be prompted via computerized instructions to take four timed puffs of the cigarette and then complete the Product Rating forms (see description below). There will be a 15-min delay prior to the *Preference Phase*. During protocol breaks, participants will be allowed to watch TV or read magazines.

Product Rating Forms will be administered using Qualtrics or REDCap immediately after sampling the product:

- 1) MNWS
- 2) QSU-10 Usual Brand Version
- 3) PANAS
- 4) CES- Study Cigarette Version
- 5) PHRS- Study Cigarette Version
- 6) Cigarette Purchase Task –Study Cigarette Version

Preference Phase Procedures

After the *Sampling Phase* has been completed, participants will complete the *Preference Phase* (30 min), which is designed to determine the relative reinforcement value of each product. During this phase, participants undergo a series of 10 choice trials, each lasting 1 minute, with a 2-min inter-trial interval. During each trial, participants will be presented (via computer) with a choice between taking 2 puffs of the cigarette or to abstain from puffing. Indices derived from this task include: total number of cigarette puffs; and total number of choices to abstain from product use. The maximum puffing rate for this task is 20 puffs in 30 minutes.

POST-TASK Physiological measures collected, recorded on paper, and entered into REDCap by the interviewer at the end of the visit:

- 1) CO

Vaping Device Practice

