5.3. Exploratory Endpoints

- Number of choices for cigarette puffs (0 to 10)
- Number of choices for e-cig puffs (0 to 10)
- Number of choices to abstain from puffing (0 to 10)
- Measures of compliance: drop-out rate
- Measures of discomfort/dysfunction: MNWS, QSU, PANAS
- Measures of cigarette characteristics: CES, Cigarette Purchase Task indices
- Measures of perceived risk: Perceived Health Risk Scale
- Measures of cardiovascular function: heart rate, blood pressure
- Biomarkers: TNE, NMR, Cotinine, CO

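### The Cigarette Purchase Task cannot show what prolonged VLNC use does to demand, because participants have only brief laboratory exposure to the study cigarette

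*Combined protocol and SAP*

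**What the plan says.** The protocol, under Baseline Procedures, presents the Cigarette Purchase Task as a source of demand curves and of indices such as demand intensity and breakpoint. Its last sentence begins: "This task will indicate whether prolonged VLNC cigarette use reduces cigarette demand". The rest of that sentence makes the same claim for sensitivity to price.

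The rest of the plan fixes how the task is used:

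- **Version.** The item carrying that sentence is the "Cigarette Purchase Task – Usual Brand Version". Lab Session 1 lists the "Cigarette Purchase Task –Study Cigarette Version". Lab Sessions 2-4 and Lab Session 5 list study-cigarette and vaping-device versions. No session after Baseline lists a usual-brand version of this task.
- **Timing.** "Product Rating Forms will be administered using Qualtrics or REDCap immediately after sampling the product". In Session 1 participants are prompted to "take four timed puffs of the cigarette and then complete the Product Rating forms". Later sessions do the same for the cigarette and then for the device. The Preference Phase always follows the ratings.
- **Between sessions** (protocol, Overall Study Design): "Between lab sessions, participants will be instructed to return to their usual tobacco use patterns".
- **Status.** Both the protocol's Outcome Variables and SAP 5.3 place the task among the exploratory endpoints. The SAP entry reads "Measures of cigarette characteristics: CES, Cigarette Purchase Task indices". SAP 6.5 does not name the task in its own list. Its general rule, a linear mixed model for anything measured repeatedly across lab sessions, would cover it, but that section names no baseline adjustment.

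**The concern.** To learn what prolonged VLNC use does to demand, participants must smoke VLNC cigarettes over a sustained period and demand must be measured afterwards. Here the study cigarette is smoked only in the laboratory, in short bouts, between periods of ordinary tobacco use.

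The protocol says, under Expected Benefits, that the findings may inform FDA regulation. Demand after brief sampling and demand after sustained use are different claims for that purpose. A VLNC-NNC difference reported under the protocol's sentence would be given the wrong one of the two meanings. SAP 6.5 defines no contrast for this endpoint that would correct it.

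**Working it through.** The plan gives no figure for this endpoint and its power calculation is not tied to it, so there is nothing to reproduce. The check is a count of exposure and a comparison of the task versions.

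**Inputs.** Sampling is 4 cigarette puffs per session (Sampling Phase, Lab Sessions 1 to 5). The Preference Phase has 10 choices of 2 puffs, so at most 10 × 2 = 20 cigarette puffs (protocol Preference Phase; SAP 5.1). A session therefore gives between 4 and 4 + 20 = 24 study-cigarette puffs. The low end applies if every choice is to abstain or, from Session 2, goes to the e-cigarette.

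**Exposure when the task is completed in session s.** The task comes after sampling and before the Preference Phase, so:

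- minimum = 4s
- maximum = 24(s − 1) + 4

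| Session | Minimum puffs | Maximum puffs |
|---|---|---|
| 1 | 4 | 4 |
| 2 | 8 | 28 |
| 3 | 12 | 52 |
| 4 | 16 | 76 |
| 5 | 20 | 100 |

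**Calendar time.** Sessions are at least 48 hours apart, so the four gaps span at least 4 × 2 = 8 days. Those days are not VLNC exposure, because participants are told to use tobacco as usual. The instruction does not literally say usual brand. For daily or near-daily smokers who receive the study cigarette only in the laboratory, this makes no difference.

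**The protocol's own yardsticks.** Its background cites VLNC use for 11 days in an inpatient unit and for 6 weeks in outpatients. Its exclusion criteria treat a switch to research cigarettes for longer than one week as what disturbs a stable smoking baseline. No participant in this trial is switched.

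**Could any contrast in the collected data support the sentence?**

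- *Usual-brand demand before and after VLNC exposure:* not available, since that version is given only at Baseline.
- *Baseline to session within the VLNC arm:* the product rated changes from usual brand to study cigarette. The sessions also follow overnight abstinence, which Baseline does not require. Exposure cannot be separated from either.
- *Session 1 to Session 5, study cigarette, within the VLNC arm:* same product, but at most 100 − 4 = 96 further puffs, and e-cigarettes are added from Session 2.
- *VLNC versus NNC on the study-cigarette version:* randomized and valid, but it estimates demand after the exposure in the table.

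None of these estimates an effect of prolonged use.

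**The case against.** The strongest reply is that this is one inaccurate word in the description of an instrument. Both documents class the task with measures of cigarette characteristics, and the lab-session procedures list it among the product ratings, so the intended reading is largely there already. The SAP makes no claim about prolonged use, and the endpoint is exploratory. All of this stands and keeps the point small. It does not remove it: the protocol still states an inference that the data cannot support, and SAP 6.5 leaves the purchase-task contrast undefined.

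A reader might infer more than the documents support:

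- *That change from Baseline is a confounded planned analysis.* Neither document plans a change score for this task. Nor would the switch of product bias a comparison of arms. The difference in mean change equals the session difference between arms minus the Baseline difference between arms. The latter has expectation zero under randomization, and both arms make the same switch. The problem is confined to a change within one arm.
- *That the task is uninformative or the design at fault.* The randomized comparison is sound for the narrower question, and no data collection needs to change.
- *That the task captures only a first reaction to an unfamiliar cigarette.* This fits Session 1. By Session 5 a participant may have taken up to 100 puffs of the same cigarette.
- *That the main conclusions are at risk.* They do not use this endpoint.

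**Conclusion.** The point holds as a minor one about stated inference and an undefined analysis. The purchase task can compare demand and price sensitivity for the assigned study cigarette after brief laboratory exposure: 4 puffs at Session 1, rising to between 20 and 100 by Session 5. It cannot show the effect of prolonged VLNC use.

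This assumes that participants take the sampling puffs as prompted, attend all sessions, and smoke the study cigarette only there. The documents set no threshold for prolonged use, and the conclusion needs none, since exposure is confined to five separate sittings with usual tobacco use between them.

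**What to change.** **Protocol, Baseline Procedures, Cigarette Purchase Task.** Replace the last sentence with wording along these lines: *The usual-brand version at Baseline provides a baseline demand index. The versions given in the lab sessions compare demand, and sensitivity to price, for the assigned study cigarette (and, in Sessions 2-5, the vaping device) after brief laboratory sampling.* This removes *prolonged* while keeping price sensitivity and the vaping-device version. It also avoids tying the description to four puffs alone, which is exact only for Session 1.

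**SAP 6.5.** Name the purchase-task indices. Define the VLNC-NNC contrast on the study-cigarette version, including which sessions enter it. Add the usual-brand Baseline index as a covariate. This follows SAP 6.4, which already adds baseline values for precision. With a correlation ρ between the Baseline and session indices, adjustment multiplies the residual variance by about 1 − ρ². The documents give no ρ, so the gain is not quantified here.

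**Cost.** Wording only; data, visits and sample size are unchanged. The price is a narrower claim from an exploratory endpoint. As the SAP is marked final, the definition should go into a dated addendum that states whether it preceded analysis of this endpoint.
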